5.2.6 Dependency

Lawton Instrumental Activities of Daily Living Scale, (L-IADL). The L-IADL is a valuable tool completed by the clinician to assess patients with early-stage disease, both to assess the level of disease and to determine the patient's ability to care for him or herself. Performance of IADLs requires mental as well as physical capacity. The IADL scale measures the functional impact of emotional, cognitive, and physical impairments and their need for personal care services. IADLs are scored based on what an individual can do rather than what he/she is doing. IADLs are scored based on how an individual usually performs each of eight tasks. The tasks assessed include: telephone use; food preparation; shopping; housekeeping; laundry, transportation mode; responsibility for own medication and ability to handle finances. The patient receives a score of 1 for each category item if his or her competence is rated at some minimal level or higher, or a score of zero if below minimum capacity. The total sum of scores may range from 0 – 8. A lower score indicates a higher level of dependence. This form can be completed in approximately 5 minutes by the clinician using patient hospital file & Interview

5.2.7 De Jong Loneliness

The development and testing of an explanatory loneliness model were described in De Jong Gierveld (1987 & 1998). A 6 item validated version of the **loneliness scale** was developed by De Jong Gierveld & Van Tilburg (2006), three questions assessing social isolation and 3 on emotional loneliness. The scale may be used in face-to-face interviews, telephone interviews, self-administered (mail) questionnaires, as well as in electronic data collection. It is recommended by developers that the scale be presented somewhere in the middle of the interview or questionnaire style; that is, at a moment when a considerable degree of self-disclosure from the respondents may be expected. Ideally, questions about characteristics of the respondents' networks of social relationships should precede the scale items.

The model is based on the so-called cognitive theoretical approach to loneliness. Characteristic of this approach to loneliness is the emphasis on the discrepancy between what one wants in terms of interpersonal affection and intimacy, and what one has; the greater the discrepancy, the greater the loneliness. Background characteristics (such as marital status, sex and living arrangements), descriptive characteristics of the social network, number and frequency of contacts with network members, and personality and health are identified as important loneliness-provoking factors. Other factors are found to be of crucial importance as well, such as social norms and values, expectations of support associated with certain relationships, and the positive or negative evaluation of the network of relationships-as-realized.

This form can be completed in approximately 1 minute by the clinician using patient Interview.

[figure not shown]
5.2.8 Data Logging

In general, healthy aging population operate in a wide range of listening environments with listening profiles that are unique to them.

A measure of success of CI treatment is the average daily use (hrs/day). Furthermore the variety of listening environments experienced will be automatically recorded at each post implant assessments interval(s) as an indicator for social integration.

The sound processor features an in-built data-logging function. Data are extracted automatically at each programming session while the sound processor is connected to the fitting software, *Custom Sound*. Information on daily usage is saved into the local Custom Sound data base at the clinic. Subsequently the individual daily usage data can be exported through a software function (i.e. as CDX files), with the patient's details kept anonymous. Specifics of the data to be collected at each programming session includes the print screen below & additional record of:

- Connection to Custom Sound Date
- Number of days since last connection to Custom Sound
- Average Time on air per day
- Average Time in Noise, Speech in Noise, Speech, Quiet, Music, Wind

There is no form to be completed for data logging as data are contained within the CDX file exported. The investigator will send the anonymized exported CDX file after the 18-month visit has been completed to the sponsor using the Patient ID code as the file name (e.g. PatientID.CDX)

5.2.9 Patient profile data

Coded demographic data will be collected via a customized case report that is completed by the clinician. The information is used to profile and describe the patient group characteristics in terms of audiological history, telephone use, living environment and educational level at the preimplant interval.

Data gathered will be summarized for the group. Select variables may be examined for correlation with one or more outcomes.

This form can be completed in approximately 5 minutes by the clinician using the patient's hospital file & via interview.

5.2.10 Healthcare Resource Utilization (HRU) data

General Healthcare data. A customized case report is completed by the clinician.

This questionnaire has been designed by department of Health Economics from Gran-Canaria University (Author: [name] & [name]). It is based on general European health survey and adapted to be relevant to the CEL5671 study. The questionnaire is color coded where data in pink should be taken from the medical records and data in black are collected through interview with the Subject.

Collected data includes

- Type of health care coverage and employments status
- Use of primary care and emergency services
- Use of specialist practices and/or outpatient surgery services
- Diagnostic tests performed such as radiology, laboratory tests,...
- All hospitalization within the time period observed
- The list and dose of prescribed medication taken
- The list and dose of non-prescription medication taken
- Visits to physiotherapy and rehabilitation
- Sessions with a speech therapist
- Sessions at psychologist
- Use of social welfare care
- Whether subject has lived in a residential care home
- Use of home help or social services
- Support and help from family, friends or others

Data collected will represent the 6-Month time-frame prior to each of the 3 test intervals.

Data will be used to quantify the use of health resource across the duration of the study. The quantification will be done in the corresponding units (i.e. number of visits, exams, doses of medication, subject's health expenses,...). In a second stage and in collaboration with national experts, these quantities will be converted in health care costs.

Data obtained would potentially be used for economic modelling of direct and indirect costs in the long term related to the intervals post CI treatment and prior to CI treatment.

This form can be completed in approximately 30 minutes by the clinician using the subject's patient hospital file & via interview.

6 Risks associated with participation in the observational study

Participation in the observational study presents no additional risk to the patient over and above routine clinical care using commercially available cochlear implant devices. There is no additional clinical visit outside the routine management.

7 Objectives and hypothesis

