8.2.1 Preimplant visit 1 = Pre1

Preimplant visit 1 corresponds to the first evaluation with the full assessment battery for each subject before surgery and corresponds to his/her absolute baseline.

- Preimplant assessment before implant surgery date \leq 2 months

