8.4 End-points

Primary end-point

Change in overall health related quality of life via comparison of HUI3 multi-attribute utility scores at:

- **Post1** implant Visit compared to **Pre1** implant Visit
- **Post2** implant Visit compared to **Post1** implant Visit
- **Post2** implant Visit compared to **Pre1** implant Visit

Secondary end-points:

Change in scores on battery of evaluation tools for health related domains and overall well-being on each of the following:

MMSE, DSST & Trail B (Cognition); TUG (falls); GDS-15 (depression); iADL (independency); HHIE-S (hearing handicap); SSQ (hearing & communication ability); CAP-II (capabilities of audition); De Jong Loneliness Scale, Speech recognition tests in Quiet (daily hearing function); Speech recognition tests in Noise (daily hearing function); Consistent daily use of CI via automatic data logging (hrs/day and listening environments).

- **Post1** implant Visit compared to **Pre1** implant Visit
- **Post2** implant Visit compared to **Post1** implant Visit
- **Post2** implant Visit compared to **Pre1** implant Visit

Tertiary end point:

Changes in healthcare resource utilisation with CI treatment compared to preimplant, collected at each test interval, i.e., Pre 1, Post1 and Post 2 will be compared. Each assessment will reflect a 6 month period immediately before assessment. Data reviewed for this measure will be obtained from the customized HRU questionnaire completed by the clinician on behalf of the subject (data sources available for use will be in accordance with regional guidelines).

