8.6 Subjects

8.6.1 Inclusion Criteria

- Unilateral CI candidates with bilateral postlingual deafness with intention to treat
- ≥ 60 years at *first* unilateral cochlear implant
- Implant ear: meets all local criteria for CI treatment
- Contralateral ear: average pure tone thresholds indicate a moderately-severe to profound hearing loss (4 freq. average: 0.5, 1, 2 and 3 or 4 kHz >56 dBHL).
- Willingness to participate in and to comply with all study procedures
- Fluency in languages used to assess clinical performance
- Appropriate expectations from routine CI treatment
- Able to decide on study participation personally and independently sign their consent

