8.6.2 Exclusion Criteria

- Significantly/severely dependent or fragile
- Unable to provide consent personally
- Unable to complete questionnaires for self-assessment independently
- Unilateral hearing loss
- Sequential and simultaneous bilateral cochlear implant recipients
- Ossification or other cochlear anomalies preventing full electrode insertion
- Retro cochlear or central origins of hearing impairment.
- Significant comorbidities preventing study participation (e.g. blindness, immobility or in a wheel chair, severe aphasia,..)
- Medical contraindications to surgery
- Clinically standard fail criteria for CI candidacy in regards to chronic depression, dementia, and cognitive disorders.
- Unrealistic expectations on the part of the subject, regarding the possible benefits, risks and limitations that are inherent to the procedure and prosthetic device.

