CI treatment significantly impacts healthy aging domains and wellbeing of elderly individuals compared to their pre-implant condition (and again from 12 to 18 months following surgery) as measured by clinically standard evaluation tools in the geriatric and audiological fields (as described above)

Tertiary hypothesis

CI treatment significantly reduces healthcare resource utilisation in elderly individuals over time.

Other hypotheses

There are covariates associated with the change in health-related quality of life and other healthy aging domains and related well-being.

4. Study Design

The study is a prospective observational longitudinal study performed to evaluate the benefits for overall health following CI treatment in the elderly population treated in routine clinical practice. Multiple centres are included in the study

Implantation with commercially available cochlear implant devices (i.e. products approved for market release) available for routine clinical treatment of deafness in all ages in collaborating investigator clinic sites is made as part of the study and no additional interventions are applied.

Change in outcome scores for various standard assessment tools and health domains post CI treatment compared to the pre-implant status are made using participants as their own controls. All questionnaires of interest are administered at each visit (up to 2 months pre-implant, 12 months post-implant [+/- 1 month] and 18 months post-implant [+/- 1 month]).

Whilst a recommended evaluation schedule is provided, participating clinics may select the optional evaluation measures they wish to use for their patients from the tools made available on the study specific electronic platform at baseline registration of each patient.

Participating in the study is voluntary and the participant is free to electively cease participation in the registry at any time. To be included in the study, participants must meet all local and study specific inclusion criteria and have none of the exclusion criteria. Participants remain in the study for a period of up to 2 years.

5. Sample size

Assuming that a paired t-test of the change in HUI3 multi attribute score from pre-implant to 12 or pre-implant to 18 months following implantation is of interest, then with 90% power and a 5% level of significance a change of 0.1 with standard deviation of change equal to 0.25, would require 68 participants.

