| AP7 | Who accompanies you? Primary care Emergency | Categorical (nominal) Categorical (nominal) |
| ES1 | Number of visits to specialists Type of specialist Number of visits | Categorical (nominal) Discrete |
| ES2 | Number of outpatient or day procedures Type of procedure Number of occurrences | Categorical (nominal) Discrete |
| ES3 | How to travel to specialist/outpatient centre? | Categorical (nominal) |
| ES4 | How long to travel to centre by foot? | Categorical (ordinal) |
| ES5 | Cost of travel to specialist/outpatient centre | Continuous |
| ES6 | Specialist/outpatient centre out of pocket cost | Continuous |
| ES7 | Who accompanies you to specialist/outpatient centre | Categorical (nominal) |
| PD1 | What type of functional/special tests (by test) Number of tests Number of tests due to ears Out of pocket cost of tests | Categorical (nominal) Discrete Discrete Continuous |
| | What type of radiology (separately by test) Number of tests Number of tests due to ears Out of pocket cost of tests | Categorical (nominal) Discrete Discrete Continuous |
| | What type of laboratory tests (separately by test) Number of tests Number of tests due to ears Out of pocket cost of tests | Categorical (nominal) Discrete Discrete Continuous |
| | In hospital tests in last 6 months Admission and discharge dates DRG code Hired person accompanying? Family accompanying? | Dates ¹ Categorical (nominal) Categorical (nominal) Categorical (nominal) |
| | Out of pocket costs for hospitalization in last 6 months Not related to hearing Related to hearing | Continuous Continuous |
| | Prescription medications taken (per type) Start and end date Daily dose Proportion out of pocket Cost per month Related to hearing? | Categorical (Nominal) Dates ² Continuous Continuous Continuous Categorical (binary) |
| | Non-prescription medications taken (per type) Start and end date Daily dose Proportion out of pocket Cost per month Related to hearing? | Categorical (Nominal) Dates ² Continuous Continuous Continuous Categorical (binary) |
| PHT1 | Received physiotherapy/rehab in last 6 months | Categorical (binary) |
| PHT2 | How many weeks of physio/rehab? | Discrete |
| PHT3 | Days per week of physio/rehab? | Discrete |
| PHT4 | Hours per day of physio/rehab? | Continuous |
| PHT5 | Percentage of sessions due to ear-related problems | Continuous |
| PHT6 | Had out of pocket costs for physio/rehab? | Categorical (binary) |
| PHT7 | How much out of pocket per month? | Continuous |

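### The Pre1 healthcare-use window probably contains CI candidacy work-up, which biases the pre/post contrasts for specialist visits and diagnostic tests towards a reduction

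*Protocol*

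**What the plan says.** **Windows.** Protocol 5.2.10 sets the look-back: "Data collected will represent the 6-Month time-frame prior to each of the 3 test intervals". Protocol 8.4 repeats it for the tertiary endpoint: "Each assessment will reflect a 6 month period immediately before assessment". Protocol 8.2.1 defines Pre1 as a "Preimplant assessment before implant surgery date", by no more than 2 months. Post1 and Post2 are at 12 and 18 months after surgery, each within a month.

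**Who is enrolled.** Protocol 8.6.1 admits CI candidates with an intention to treat and requires "Implant ear: meets all local criteria for CI treatment". Protocol 8.6.2 excludes, among others, "Retro cochlear or central origins of hearing impairment", cochlear anomalies that prevent full insertion, medical contraindications to surgery, and failure of the clinic's candidacy criteria on depression, dementia or cognition.

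**What is counted.** Protocol 5.2.10 and SAP section 6, Table 2 count specialist visits, outpatient procedures, radiology, laboratory and functional tests, and psychologist, speech therapy and rehabilitation sessions. For diagnostic tests the form also records "Number of tests due to ears". Table 2 lists a similar count for primary and emergency care and hearing-related fields for several other items. It lists none for specialist visits (ES1) or outpatient procedures (ES2).

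**What is claimed.** The SAP's tertiary hypothesis is that "CI treatment significantly reduces healthcare resource utilisation in elderly individuals over time". Protocol 7.1 links lower use than before implantation to possible cost savings. Each subject is their own control (Protocol 8.5). The tertiary part of SAP 7.3 Statistical Analyses carries over the primary approach for continuous outcomes and chooses other models by type of response. It has no rule for candidacy work-up.

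**The concern.** The tertiary comparison treats Pre1 use as what the subject would use without an implant. Part of it is probably use needed to decide on and prepare for the implant. That part is a one-off cost of CI treatment, but the plan books it to the comparator. When it ends, the affected items fall even if the implant changes nothing about the subject's other care.

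There is no concurrent control group in which the same fall could be seen. The results are intended for health care policy makers and may feed economic models (Protocol 3 and 5.2.10), so a fall in specialist or diagnostic use could be quoted as a saving when it is only the end of the work-up.

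**Working it through.** **1. No plan figure to reproduce.** The documents give no mean, SD, effect or sample size for HRU. The stated sample sizes of 68 and 88 concern the HUI3 multi-attribute score and do not bear on this point.

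**2. Windows, in months from surgery.** Each window runs from (visit − 6) to the visit.

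| Visit | Allowed time | Earliest window | Latest window |
|---|---|---|---|
| Pre1 | −2 to 0 | −8 to −2 | −6 to 0 |
| Post1 | 11 to 13 | 5 to 11 | 7 to 13 |
| Post2 | 17 to 19 | 11 to 17 | 13 to 19 |

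Only the Pre1 window lies before surgery, so only it can contain work-up for this implant.

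**3. Eligibility set against the HRU items.** The documents do not say which contacts establish candidacy. The natural match, which is an inference, is:
- cochlear anatomy and retrocochlear or central origin: radiology and functional tests;
- contraindications to surgery: laboratory tests and specialist visits;
- depression, dementia and cognition: specialist or psychologist contacts.

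All of these are HRU items.

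**4. What the contrast estimates.** Let u be usual use per 6 months, w the work-up use in the Pre1 window, f the CI follow-up use in a post window, and e the true effect on usual use.
- Pre1 mean = u + w
- Post mean = u + f + e
- Post − Pre1 = e + f − w

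With e = 0 the expected change is f − w. For an item with no follow-up use (f = 0) it is −w. Post2 − Post1 contains no w.

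**5. Illustration on assumed figures.** Take u = 3 contacts and e = 0. Relative change = (f − w)/(u + w).

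| | f = 0 | f = 2 | f = 4 |
|---|---|---|---|
| w = 2 | −2/5 = −40% | 0/5 = 0% | +2/5 = +40% |
| w = 4 | −4/7 = −57% | −2/7 = −29% | 0/7 = 0% |

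The first column describes an item that follow-up does not touch. The other two show why overall use can move either way.

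**6. Chance of a significant reduction when e = 0.** This uses a paired t-test, two-sided 5%, with noncentrality (net excess in Pre1 × √N)/SD of change. For an excess of 2, SD 5 and N = 100 the noncentrality is 2 × 10/5 = 4. The excess and SD, both in contacts, are assumed.

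| N | Net excess w − f | SD 3 | SD 5 | SD 8 |
|---|---|---|---|---|
| 100 | 0 | 2.5% | 2.5% | 2.5% |
| 100 | 1 | 91% | 51% | 24% |
| 100 | 2 | >99% | 98% | 70% |
| 90 (10% attrition) | 1 | 88% | 47% | 22% |
| 90 (10% attrition) | 2 | >99% | 96% | 65% |

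A net excess of one or two contacts per subject would be enough to produce a positive finding often. Whether the real excess is that large cannot be read from the documents.

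**The case against.** - **Timing is not documented.** The eligibility criteria say what must be true of a subject, not when it was established. With a long wait for surgery, part of the work-up could precede a window that opens 6 to 8 months before it. This stands: the overlap is probable, but its extent is unknown. Nor does the hearing aid trial in Protocol 5.2.2.4 settle it. That applies only to subjects tested unaided in both ears, and such a trial is also ordinary care for hearing loss.
- **CI also adds use afterwards.** Protocol 5.2.8 describes programming sessions, and the HRU form counts speech therapy and rehabilitation. A reader might infer that total use must fall even if the implant does nothing. The documents do not support that, since f may equal or exceed w. The offset does not rescue the single items, however. Table 2 lists them as separate variables, and speech therapy sessions do not restore a fall in radiology.
- **The SAP already lists ear-related counts.** They can be analysed as outcomes in their own right, and no total-use composite is defined. It would be wrong to say the plan ignores them. What is missing is a rule that uses them to separate work-up from usual care. The separate procedure document may guide completion of the form, but it is not among the documents reviewed.
- **The endpoint is tertiary.** The protocol's wording on savings is cautious, and costing is left to a later stage. This lowers the priority of the point but does not remove it, because the SAP hypothesis claims a significant reduction outright.

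**Conclusion.** The concern holds in a limited form. Work-up that falls in the Pre1 window biases the Pre1 versus Post1 and Pre1 versus Post2 contrasts for specialist visits and diagnostic tests towards a reduction, and nothing in the plan removes it. This rests on one inference: that candidacy is established, at least in part, within the 6 months before a visit held at most 2 months before surgery. That is likely given the eligibility rules, but it is not stated, so confidence is moderate.

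The size cannot be computed, and the figures in the working are illustrations only. The conclusion is firmest for diagnostic tests. For specialist visits, any follow-up visits recorded under the same item would offset part of the bias. For overall use the net direction is open. A reader might also conclude that all use coded to ears should be dropped from the main comparison. The documents do not support that either: it would remove genuine ear-related effects of CI, and could still leave in work-up on surgical fitness or cognition that is not coded to ears.

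**What to change.** In the tertiary part of SAP 7.3 Statistical Analyses, and in Protocol 8.4, pre-specify the following.

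1. HRU items done to establish CI candidacy are identified from the existing ear-related and hearing-related fields, type of specialist, type of test and the medical records.
2. Each Pre1 versus Post1 and Pre1 versus Post2 comparison is reported with and without these items.
3. CI follow-up use (fitting, rehabilitation, speech therapy) is shown separately.
4. Any costing counts work-up as a cost of CI treatment.
5. No savings claim is made for an item whose fall disappears once candidacy items are removed.

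**Cost.** The change needs SAP and protocol wording, a derivation rule and some review of records. It changes no visit, treatment or sample size. Attribution will be imperfect: ES1 and ES2 list no ear-related count, so type of specialist or procedure and the records must serve, and part of the data comes from interview. Subjects already enrolled need retrospective classification. Counted from the study start in November 2017, about 25 of the 31 enrolment months had passed when the current protocol version was issued in December 2019.
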